The proposed project addresses these unmet needs by testing a novel intervention to improve the treatment of OUD patients hospitalized for medical reasons. The intervention will

combine 1) medication-assisted treatment with buprenorphine initiated in the hospital, 2) care management to address domains known to improve transitions of care (monitoring and managing symptoms, encouraging self-management skills, and enlisting community and social supports⁴⁰⁻⁴³), and 3) recovery coaches to assist the patient in the community after discharge from the hospital. Previous studies lacked one or more of these components, or were not focused on OUD patients. While the use of buprenorphine has been studied with hospitalized patients, previous studies did not provide longitudinal support in the community following discharge.^{34,36} Previous studies on transitions of care have not specifically targeted hospitalized OUD patients, even though drug use is a well-known risk factor for readmissions.⁷ Care management has been frequently utilized to manage complex patients, but no prior studies have targeted hospitalized OUD patients being discharged into the community. Finally, recovery coaches have also not been studied to improve treatment retention of OUD patients treated with buprenorphine⁵⁹. In this study, the trainings and responsibilities of the recovery coach and care management will be merged into one role. Further, this study brings these promising elements together into one novel model. If successful, this model could prove useful for engaging hospitalized out-of-treatment OUD patients.

II. Aims:

Our hypothesis is that the recovery coach intervention will be associated with greater success not only in remaining in treatment, but also in reducing the likelihood of hospital readmissions.

Specific Aim #1: To assess whether subjects randomized to the recovery coach intervention will demonstrate greater retention in treatment and better opioid use outcomes at 24 weeks compared to control subjects in a randomized controlled trial.

Hypothesis 1a: Subjects receiving the intervention will be more likely to remain in treatment at 24 weeks, as compared to control subjects.

Hypothesis 1b: Subjects receiving the intervention will report fewer days of illicit opioid use in the prior 30 days at 24 weeks, as compared to control subjects.

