Post-discharge component: Following discharge, the recovery coach will meet with the participant up to 3 hours per week (**Table 2**). Each recovery coach will carry a caseload of no more than 3 participants at a time. More frequent contact will be permissible if the care team needs to respond to emergencies or other clinical issues requiring additional contacts. For participants who may live outside of Boston or are otherwise unable to return to the Brigham Hospital area, the recovery coach will meet with participants via phone call or video conferencing. Each week, the coaches will conduct peer-led individual sessions using topics adapted from the MISSION-VET manual. The recovery coaches will encourage the continuation of treatment and accompany participants to appointments if necessary, and function as a liaison between the participant and the clinicians. The coaches will help determine recovery goals, share and suggest coping strategies, and model healthy living. The coaches will also instill hope through example, and provide support during crises. The coaches will assist with linkage to community programs, and assist with essential life skills such as setting up a bank account or using public transportation. The candidate will meet

weekly with the recovery coaches to review each case. If the participant successfully linked with the BWH-affiliated buprenorphine clinic, retention in treatment will be confirmed with the clinic.

Fidelity: The MISSION Fidelity Index from the MISSION-VET manual⁶⁸ will be adapted for this study to ensure intervention fidelity. The index is designed to document services delivered as indicated in the manual.

Compensation: Participants will be reimbursed \$50 for the baseline, 4- and 12-week follow-up visit, and \$100 for the 24-week visit.

Schedule of Assessments: Baseline measures will be obtained during the hospitalization. Follow up assessments will occur at 4, 12 and 24 weeks after discharge. A research assistant blinded to study assignment will collect all data. Patients who are unable to return to the hospital for the follow-up assessments will complete their measures via phone call or Partners Enterprise Zoom (if participant prefers) with the research assistant.

Measures: As recommended by notice NOT-DA-12-008, measures from the Substance Abuse and Addiction Collection of the PhenX Toolkit were chosen where appropriate. The schedule of assessments is summarized in **Table 3**.

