- Demographic measures (Core Tier 1 measures): A questionnaire to collect demographic information on age, gender, ethnicity, marital status, employment, housing, education, and socioeconomic status.
- Mini-International Neuropsychiatric Interview (MINI)⁷²: A brief structured psychiatric diagnostic interview that was designed to permit the rapid diagnosis of the major psychiatric disorders.
- Pregnancy test: Females will undergo pregnancy testing at the time of screening.
- Stages of Change Readiness and Treatment Eagerness Scale (SOCRATES)⁷⁴: To assess readiness.
- Urine toxicology: Routine urine immunoassay screen will be obtained to assessed, including opioids. These will be obtained during routine clinical visits, separate from study visits.
- Addiction Severity Index 5th edition (ASI)⁷⁵: The ASI will assess multiple dimensions of SUD.
- Opioid craving^{76,77}: A single-item questionnaire will be used to determine craving for opioids.
- Patient Health Questionnaire 9-item (PHQ9)⁷⁸: This questionnaire will assess depressive symptoms.
- Brief Pain Inventory⁷⁹: Pain severity and the degree to which pain interferes with life will be assessed.
- Time-line follow back (TLFB)⁸¹: Assess past 30-day use of substances.
- Verification of treatment retention: Treatment retention will be verified by the BWH/BWFH-affiliated clinic.
- The Health-Care Climate Questionnaire - Recovery Coach version (HCCQ-RC): A brief 15-item measure added to assess patients' perceptions of the degree to which they experience their recovery coach to be autonomy supportive.
- Adverse Childhood Experiences International Questionnaire (ACE-IQ): A survey designed to collect information from adults about events they experienced in the first 18 years of their lives, including family dysfunction and exposure to violence.
- Health-Care Climate Questionnaire – Hospital Care Team Version (HCCQ-HCT): A brief 15-item measure added to assess patients' perceptions of the degree to which

they experienced the hospital care team (e.g. nurses, doctors, social workers) to be autonomy supportive.

- PTSD Checklist (PCL-5): A 20-item self-report measure that assesses the presence and severity of PTSD symptoms, corresponding with DSM-5 criteria for PTSD.
- Brief Addiction Monitor (BAM): A 17-item, progress-monitoring instrument for patients in treatment for a substance use disorder, used to assess risk factors for substance use, protective factors that support sobriety, and drug and alcohol use.

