Sample size/power analysis: In a study of a care management intervention for patients with substance use disorder in primary care, individuals receiving the intervention were more likely to remain in treatment at 24 weeks (40% vs 10%).⁵² While this study is entirely community based, no other comparable studies have been conducted with OUD patients on buprenorphine. Based on this effect size, we plan to screen 145 participants, assuming a 60% attrition due to screening failure, allowing for a sample size of 58 available for analysis, evenly divided between the control and intervention arm. This will yield a statistical power of 0.8 and 95% confidence level to detect differences in proportions of participants who remain in treatment at 24 weeks, as confirmed by the BWH-affiliated clinic. The study will not be powered to detect smaller effect sizes, but will be helpful in providing important information about effect sizes to adequately power future studies.

Specific Aim #1: The hypothesis that participants receiving the intervention will be more likely to remain in buprenorphine treatment at 24 weeks will be tested using logistic regression, treating the endpoint as a categorical variable. Treatment retention data will be obtained directly from the BWH/BWFH affiliated buprenorphine clinics. The hypothesis that participants receiving the intervention will report fewer days of illicit opioid use at 24 weeks will be tested using mixed effects ANOVA modeling, treating the endpoint as a continuous variable. ANCOVA will be used to adjust for relevant covariates, including age, sex, ethnicity/race, and baseline illicit opioid use. Illicit opioid use will be determined from the TLFB and urine toxicology results.

Specific Aim #2: The hypothesis that participants receiving the intervention will be less likely to be readmitted at 24 weeks will be tested using logistic regression, treating the endpoint as a categorical variable. Readmission data will be obtained from the ASI and GAIN service utilization items.⁸⁰ Results will be adjusted for relevant covariates, including demographic variables and baseline clinical variables. While 30-day readmission rate is an important metric for hospitals, the readmission rate at 24 weeks may better evaluate the impact of the proposed intervention.

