- b. Measurement and reporting of participant adherence to treatment protocol: Data on adherence to the treatment protocol will be collected weekly by research staff and reviewed quarterly by the PI. Fidelity to the treatment manual will be reviewed by the candidate each week with the recovery coaches.

3. Justification of sample size: In a study of a care management intervention for patients with substance use disorder in primary care, individuals receiving the intervention were more likely to remain in treatment at 24 weeks (40% vs 10%). While this study is entirely community based, no other comparable studies have been conducted with OUD patients on buprenorphine. Based on this effect size, we plan to screen 145 participants, assuming a 60% attrition due to screening failure, allowing for a sample size of 58 available for analysis, evenly divided between the control and intervention arm. This will yield a statistical power of 0.8 and 95% confidence level to detect differences in proportions of participants who remain in treatment at 24 weeks, as confirmed by the BWH-affiliated clinic. The study will not be powered to detect smaller effect sizes, but will be helpful in providing important information about effect sizes to adequately power future studies.

4. **Stopping rules:** This study will be stopped prior to its completion if: (1) the intervention is associated with adverse effects that call into question the safety of the intervention; (2) difficulty in study recruitment or retention will significantly impact the ability to evaluate the study endpoints; (3) any new information becomes available during the trial that necessitates stopping the trial; or (4) other situations occur that might warrant stopping the trial
5. **Designation of an independent monitor:** To minimize any conflicts of interest, a physician from Brigham and Women's Hospital familiar with clinical research who is not a collaborator or investigator on the proposed project, nor a close colleague, will serve as an independent individual to monitor the data and safety.

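### Hypothesis 1a is about remaining in treatment, but retention is ascertained only at the BWH/BWFH-affiliated clinics and missing retention counts as discontinuation, so a participant retained elsewhere is scored as a failure

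*Combined protocol and SAP*

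**What the plan says.** **Hypothesis.** Section II, Hypothesis 1a: "Subjects receiving the intervention will be more likely to remain in treatment at 24 weeks, as compared to control subjects". It limits neither the clinic nor the type of treatment.

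**Treatments in scope.** Sections III and IV admit patients willing to enter a psychosocial programme and/or to take methadone or buprenorphine. In Section V, the referral text for both arms speaks of buprenorphine or methadone having been started and provides methadone-programme contacts as well as intake numbers for the affiliated buprenorphine programmes. Section VII (Buprenorphine medication safety), by contrast, has every subject begin buprenorphine before being randomized.

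**Endpoint as tested.** Section VI, Specific Aim #1, says participants in the intervention arm will be "more likely to remain in buprenorphine treatment at 24 weeks will be tested using logistic regression".

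**Source of retention data.** Four places besides Hypothesis 1a address it, and all name the affiliated clinics:
- Section VI, Specific Aim #1: "Treatment retention data will be obtained directly from the BWH/BWFH affiliated buprenorphine clinics".
- Section V, Measures: "Treatment retention will be verified by the BWH/BWFH-affiliated clinic".
- Section V, Post-discharge component: "If the participant successfully linked with the BWH-affiliated buprenorphine clinic, retention in treatment will be confirmed with the clinic". Nothing is said about participants who link elsewhere.
- The sample-size text in Section VI, where the power is to "detect differences in proportions of participants who remain in treatment at 24 weeks, as confirmed by the BWH-affiliated clinic". Section IX, item 3, repeats it.

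**Missing data.** Section VI scores absent retention data as having stopped treatment. It also promises to record reasons for missingness and to compare results under other methods, without naming a method.

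**The concern.** The hypothesis and the measurement do not cover the same people. Someone still in methadone or psychosocial treatment, or on buprenorphine at an unaffiliated clinic, satisfies Hypothesis 1a as written but has no stated route to being counted as retained.

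This matters because retention is the only endpoint with a stated power, and Section VI says the trial's effect sizes will help to power later studies. Depending on what 40% vs 10% refers to, either power is lost or the effect size carried forward is for something narrower than the hypothesis.

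**Working it through.** **Step 1. How a participant retained elsewhere is scored.** There are two possibilities. Either the affiliated clinic holds no record, so retention is missing and the imputation rule gives discontinuation; or the affiliated clinic reports the person as not in its care. Both give a failure. No single sentence says this; it follows from combining the source and imputation rules.

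**Step 2. Whether another instrument rescues it.** For Aim 2, Section VI says: "Readmission data will be obtained from the ASI and GAIN service utilization items". No text assigns either instrument to retention. The ASI is scheduled at every assessment from baseline in Table 3; GAIN appears in neither the measures list nor Table 3.

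**Step 3. The plan's own figure.** Inputs from Section VI are 40% vs 10%, power 0.80, 95% confidence, equal arms and 58 analysed. A two-sided test is assumed, since sidedness is not stated. With the unpooled two-proportion formula:

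n per arm = (1.960 + 0.842)² × (0.40×0.60 + 0.10×0.90) / 0.30² = 7.85 × 0.33 / 0.09 = 28.8, rounded up to 29. Total 58, and 145 × 0.40 = 58.

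Power at 29 per arm = Φ(0.30 / √(0.33/29) − 1.960) = Φ(0.85) = 0.80. The sample-size arithmetic is sound.

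**Step 4. Reading A: 40% vs 10% are retention rates at any clinic.** Let c be the share of truly retained participants whom the affiliated clinics can confirm, equal in both arms. Observed rates are then 0.40c and 0.10c. The documents give no value of c, so those below are assumptions.

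| c | Observed rates | Difference | Power, 29 per arm (unpooled) | n per arm for 0.80 |
|---|---|---|---|---|
| 100% | 40% vs 10% | 30 points | 0.80 | 29 |
| 90% | 36% vs 9% | 27 points | 0.74 | 34 |
| 80% | 32% vs 8% | 24 points | 0.67 | 40 |
| 60% | 24% vs 6% | 18 points | 0.51 | 58 |

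For c = 80%: Φ(0.24 / √((0.32×0.68 + 0.08×0.92)/29) − 1.960) = Φ(0.43) = 0.67.

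Other methods start at different levels but fall in the same way over the four rows: pooled formula 0.77, 0.70, 0.63, 0.48; Fisher's exact test 0.68, 0.60, 0.52, 0.32; unadjusted logistic likelihood-ratio test 0.81, 0.75, 0.69, 0.54. The last is anti-conservative at this size (type I error about 0.076 when both arms are at 10% and 0.088 at 6%), so its levels are flattering.

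**Step 5. Reading B: 40% vs 10% are affiliated-clinic-confirmed rates.** The sample-size text is worded this way. Observed rates are then 40% vs 10% by definition and power stays 0.80. What changes is the quantity estimated: retention at affiliated clinics, not Hypothesis 1a.

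**Step 6. Capture by arm.** Table 2 gives the coach, in the intervention arm only, a task of referring to the affiliated buprenorphine clinic. The social worker's referral text is nearly the same in both arms. Capture could therefore differ by arm, but the documents allow no estimate.

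**The case against.** The strongest reply is that the plan does define its endpoint: buprenorphine retention confirmed by the affiliated clinic, with missing scored as failure. For a 58-person trial, a clinic-verified outcome is coherent, and the stated power then holds. The background, Section VII and Section VIII all frame the study around buprenorphine started in hospital. On that view methadone and psychosocial retention are not missed outcomes, and no text refers anyone to a named unaffiliated buprenorphine clinic.

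Much of this stands. It is Reading B, and it reduces the defect to a mismatch between endpoint and hypothesis. It does not remove that mismatch: the buprenorphine-only reading conflicts with the entry criteria and with both arms' referral text, and buprenorphine continued at an unaffiliated clinic is still lost. Nor is scoring missing as failure simply cautious here, because the record may be absent owing to where a person is treated rather than because treatment stopped.

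Some apparent support is weak and is not relied on. The methadone offer in Section IV is made at the initial screen, before full eligibility is applied. The Section V sentence on participants living outside Boston concerns how coaching is delivered. Choosing a clinic by geography may mean choosing among affiliated programmes.

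A reader might infer from the coach's referral task that the comparison is biased towards the intervention. The documents do not support that: they establish neither size nor direction. A reader might also infer that the trial is underpowered as designed; that holds only under Reading A with an assumed capture share.

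**Conclusion.** The concern holds as a mismatch between hypothesis, endpoint and data source. Following the plan as written, anyone retained outside the affiliated clinics is scored as not retained. This should be fixed before analysis, since outside-clinic outcomes may be hard to recover after follow-up ends.

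The number affected is unknown. Power of 0.74, 0.67 or 0.51 is an illustration under Reading A with equal capture of 90%, 80% or 60%. Under Reading B the stated 0.80 stands and the cost is in what is measured. The sample-size calculation itself is not at fault. Confidence is medium, because the plan leaves unclear which treatment it means and consent pages were not available to show what contact with outside clinics is already permitted.

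**What to change.** 1. Reconcile Section VII (all started on buprenorphine) with Sections III, IV and V (psychosocial, methadone or buprenorphine), then make Hypothesis 1a and the Aim 1 endpoint name the same treatment.

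2. **Preferred.** At the existing 24-week assessment, ask every participant about current treatment and clinic. Verify with the named clinic by the same procedure in both arms, with permission if consent does not already cover it. Use self-report only if the clinic does not respond, and impute discontinuation only when neither source exists. Report clinic-verified-only and affiliated-clinic-only retention as sensitivity analyses.

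3. **Minimum alternative.** If affiliated-clinic retention stays primary, reword Hypothesis 1a and the conclusion to *retention at a BWH/BWFH-affiliated buprenorphine clinic*, and report any-clinic retention as a sensitivity analysis.

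4. State that 40% vs 10% is an assumption for the chosen endpoint, and show power at a few other rate pairs.

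**Cost.** Protocol wording, one question at an existing visit, some verification calls and possibly a permission form. Some outcomes would rest on self-report from participants who know their arm. The assistant collecting it is described as blinded, but that is not secure: Section IV has the assistant randomize remotely enrolled participants, and Table 3 schedules a recovery-coach questionnaire (HCCQ-RC) at follow-up. The clinic-verified analysis checks this. Power at 29 per arm may fall below 0.80 if the broader endpoint has other rates: by the unpooled formula, 0.75 at an assumed 45% vs 15%, 0.71 at 50% vs 20% and 0.40 at 40% vs 20%.

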 - C. Enlisting community and social supports:
 - Encourage self-help group attendance
 - Review importance of establishing a support system

Session #2: (60 minutes with Recovery Coach)

- 1) Review treatment plan
- 2) Organize post-discharge appointments and problem-solve potential barriers in keeping appointments.
- 3) Reconcile discharge medication regimen.
- 4) Review the use of naloxone overdose rescue kit.
- 5) Invite family members to attend session if applicable.
- 6) Notify treatment plan to outpatient providers if applicable.

Post-discharge component (adapted from MISSION manual)

Recovery coach (2-3 hours per week of direct contact)

- 1) Assist implementing Treatment Plan and help prioritize goals
- 2) Weekly coach-led sessions utilizing the ISTOP treatment manual
 - Brief introduction to day's topic
 - Offer personal insights or a story to further setup topic
 - Questions, if needed, to spark discussion
 - A facilitated discussion on the topic
- 3) Provide support in the following areas:
 - A. Monitoring and managing symptoms:
 - Encourage continuation of buprenorphine treatment
 - Accompany participants to appointments
 - Liaison between participants and clinicians
 - B. Patient education and self-management:
 - Help determine and increase motivation for recovery goals
 - Share and suggest coping strategies
 - Reinforce relapse prevention skills
 - Recreational planning and modeling healthy living
 - C. Enlisting community and social supports:
 - Role modeling and inspiring hope
 - Provide support during crises or job stresses
 - Identify and link to community recovery programs
 - Assist with essential life skills such as setting up bank accounts, getting a driver's license, using public transit, etc

referred. The participants will be encouraged to schedule an appointment prior to discharge. Instructions on safely tapering the buprenorphine will be reviewed prior to discharge, in the event the participant does not initiate treatment before the prescription runs out. Participants will be provided with community resources including outpatient addiction programs, 12-step meetings, and referral to outpatient mental health treatment if needed. We recognize that the control group does not balance non-specific effects of the intervention (e.g. increased attention). If our finding is promising, this study will help inform better control group design to account for non-specific effects of the intervention.

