medication. Commonly reported side effects include nausea, vomiting, constipation, muscle cramps, insomnia, irritability, sweating, and fevers. Subjects will be asked to report any side effects to the study staff, hospital staff, or their buprenorphine prescriber. If these side effects are reported to study staff, the candidate will be informed and will take appropriate action. The candidate has extensive experience managing OUD patients with buprenorphine, and is well versed in the appropriate clinical management of any emergent side effects from buprenorphine. Subjects will also be advised that ingesting buprenorphine with other sedative drugs, such as benzodiazepines, dramatically raises the possibility for a synergistic reaction that can cause an overdose or even death. Individuals with any underlying liver disease or have a history of hepatitis C will be informed that buprenorphine use has been rarely associated with liver failure, and that liver function test will be obtained. Subjects will be informed that buprenorphine medication should be stored in a secure location, ideally with a lock-box, to ensure no one else can access the medication including children. Finally, studies show that after stopping buprenorphine medication, individuals are at heightened risk of relapse to illicit opioid use, as well as greater likelihood of non-fatal and fatal overdoses. As such, subjects will be counseled about the risks of relapse and overdose throughout the study period.

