Intoxication: The study population targets OUD patients, who were actively using illicit opioids prior to the hospitalization. As such, it is possible for participants to be intoxicated from illicit opioids or other substances during their work with recovery coaches or during study visits. Participants will be required to abstain from substances other than buprenorphine for at least 4 hours prior to each study visit. Intoxication will be determined through self-report and clinical observation. If a participant is intoxicated in any way, they will not be permitted to complete the visit, and the visit will be rescheduled at the earliest convenient time. Consistent with standard clinical practice, when possible, the recovery coaches will discuss with the candidate to determine the best management options. This may include notifying the inpatient/outpatient providers or family members, referring to medical treatment, calling emergency services, or escorting the participant to the Emergency Room at Brigham and Women's Hospital.

Overdose: Patients with OUD are at heightened risk from fatal and non-fatal overdoses during and after buprenorphine treatment, especially if using alcohol or sedative drugs such as benzodiazepines. As such, participants will be required to abstain from using these substances. However, given their underlying illness, some participants may still ingest these other substances during the study period. All study staff, including recovery coaches, and all participating subjects will be trained in the recognition and initial management of an overdose using the naloxone-rescue kits. Subjects will also be asked to identify family or supports that can carry the naloxone rescue kits. The candidate is a board certified addiction psychiatrist well versed in the recognition and management of overdoses, and appropriate clinical action will be taken in the event of an overdose. In addition, all recovery coaches will receive training on overdose prevention and the use of naloxone rescue kits.

VIII. Potential benefits:

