6. **Safety Review Plan:** Study progress and safety will be reviewed monthly (and more frequently if needed). Progress reports, including patient recruitment, retention/attrition, and AEs, will be provided to the Independent Monitor following each of the monthly reviews. An Annual Report will be compiled and will include a list and summary of AEs. In addition, the Annual Report will address (1) whether AE rates are consistent with pre-study assumptions; (2) reason for dropouts from the study; (3) whether all participants met entry criteria; (4) whether continuation of the study is justified on the basis that additional data are needed to accomplish the stated aims of the study; and (5) conditions whereby the study might be terminated prematurely.
7. **Study report outline for the independent monitor:** Study Report tables will be generated only from aggregate (not by group assignment) baseline and aggregate safety data for the study population. A separate Closed Safety Report, with masked group baseline and safety data, will be generated for the Independent Monitor(s) by a designated unmasked member of the team but will not be reviewed by the study team.
8. **Informed consent:** The subject (if applicable, parent/guardian) will be asked to review the study consent form. The PI or Co-Investigator (Co-I) will meet with the subject to review the form, to confirm the subject's understanding of the study, and to answer any questions the subject might have. Once the subject demonstrates understanding of the study and agrees to participate in the study, the consent will be signed in the presence of the PI (or Co-I) and a witness
9. This study does not involve any medications or devices and carries no risk of harm from such medications or devices.

X. References

1. Stein, M. D. Medical consequences of substance abuse. *Psychiatr. Clin. North Am.* **22**, 351–370 (1999).
2. Stein, M. D., O'Sullivan, P. S., Ellis, P., Perrin, H. & Wartenberg, A. Utilization of medical services by drug abusers in detoxification. *J. Subst. Abuse* **5**, 187–193 (1993).
3. Ronan, M. V. & Herzig, S. J. Hospitalizations Related To Opioid Abuse/Dependence And Associated Serious Infections Increased Sharply, 2002-12. *Health Aff. Proj. Hope* **35**, 832–837 (2016).
4. Owens, P. L., Barrett, M. L., Weiss, A. J., Washington, R. E. & Kronick, R. in *Healthcare Cost and Utilization Project (HCUP) Statistical Briefs* (Agency for Health Care Policy and Research (US), 2006).

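### After discharge, side effects and overdoses have no scheduled enquiry and only the coached arm sees study staff weekly, so by-group safety counts would be expected to tilt against the intervention

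*Combined protocol and SAP*

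**What the plan says.** Section VII (Buprenorphine medication safety) describes how side effects come to light: "Subjects will be asked to report any side effects to the study staff, hospital staff, or their buprenorphine prescriber". It then gives one onward route: "If these side effects are reported to study staff, the candidate will be informed and will take appropriate action". No route is stated for what a participant tells hospital staff or a prescriber.

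Section VII (Overdose) places coaches among study staff: "All study staff, including recovery coaches, and all participating subjects will be trained". In section V (Post-discharge component), "Following discharge, the recovery coach will meet with the participant up to 3 hours per week"; coaches hold weekly individual sessions, and the candidate reviews each case with them weekly. Controls receive treatment as usual. For both arms, "Follow up assessments will occur at 4, 12 and 24 weeks after discharge", with data collected by a blinded research assistant. Neither the list of measures nor Table 3 contains an item described as asking about medication side effects or overdose.

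Under IX.4, the first ground for stopping is that "the intervention is associated with adverse effects that call into question the safety of the intervention". Under IX.7 the independent monitor receives "A separate Closed Safety Report, with masked group baseline and safety data".

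**The concern.** When events become known because a participant mentions them, the number recorded depends on how often someone is there to hear it. Here that frequency differs by randomized arm, by design. Equal true rates could then look like harm from coaching, and a real reduction in overdose could be hidden or reversed. Masked group labels do not help: a monitor who does not know which group is coached cannot allow for its closer observation. The opposite error matters too, because a control participant's overdose or side effect between visits could go unrecorded.

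Section V concedes that the control arm does not balance attention, but it considers this only for the efficacy comparison, not for the safety data.

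**Working it through.** **1. Arm size.** Section VI: 145 screened, 60% lost at screening. 145 × (1 − 0.60) = 58, and 58 / 2 = 29 per arm. The plan's power statement is reproduced by the unpooled formula for 40% against 10%, two-sided 5%, power 0.80: n = (1.960 + 0.842)² × (0.40 × 0.60 + 0.10 × 0.90) / 0.30² = 28.8, so 29. This figure is not disputed; it is used only for the arm size.

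**2. Paths from an event to the study after discharge.**

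- Told to a coach: coaches are study staff, so the stated route to the candidate applies, backed by weekly case review. Intervention arm only.
- Told to the research assistant at week 4, 12 or 24: the same route in both arms, but no scheduled question prompts it.
- Told to hospital staff or a prescriber: no stated route to the study in either arm.

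The first path makes the difference between the arms.

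**3. Scheduled contacts after discharge.** Control: 3. Intervention: 3 plus one per week of coaching. The documents do not give the duration of coaching, so a range is shown.

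- 24 weeks: 24 + 3 = 27 (9 times control)
- 12 weeks: 12 + 3 = 15 (5 times)
- 4 weeks: 4 + 3 = 7 (2.3 times)

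**4. What three visits might catch.** Assume that events fall evenly over 24 weeks and are mentioned only if a contact follows within w weeks. The intervals before the visits are 4, 8 and 12 weeks, so the control share is [min(w,4) + min(w,8) + min(w,12)] / 24. For w = 1, 2 and 4 this is 3/24 = 12.5%, 6/24 = 25% and 12/24 = 50%. Weekly contact through week 24 would catch about 100%.

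**5. Expected recorded counts.** Assume that 40% of each arm has an event, so 29 × 0.40 = 11.6 true events per arm. Recorded events = 11.6 × detection probability. The last column is from two independent binomials.

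| Detection, intervention / control | Expected recorded events | Ratio | P(intervention count higher) |
|---|---|---|---|
| 0.8 / 0.8 | 9.3 / 9.3 | 1.00 | 0.44 (tie 0.11) |
| 0.9 / 0.8 | 10.4 / 9.3 | 1.125 | 0.57 |
| 0.9 / 0.6 | 10.4 / 7.0 | 1.5 | 0.81 |
| 0.9 / 0.4 | 10.4 / 4.6 | 2.25 | 0.95 |

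For true rates from 20% to 60% and the three unequal pairs, the last column runs from 0.51 to 0.99. Every event rate and detection probability here is an assumption; the documents give none.

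**The case against.** Several safety outcomes do not depend on volunteered reports. Tolerability is monitored in hospital in both arms. Suicidal ideation can be picked up by the PHQ-9, scheduled at every follow-up for everyone. Readmissions come from ASI and GAIN items (section VI, Specific Aim #2), and the ASI is scheduled at the same visits. Intoxication is judged partly by observation. A reader might infer that participant report is the only source of any adverse event. The documents do not support that, and the gap is narrower: medication side effects and non-fatal overdose after discharge, and perhaps emergency visits.

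A reader might also infer that stopping rule 1 turns on a by-arm count. IX.4 sets no count, ratio or test, and IX.7 does not say that the Closed Safety Report drives the rule. Moreover, section VII has all participants starting buprenorphine before randomization, so its side effects are not obviously effects of the coaching that rule 1 concerns. This stands. What can be said is that the monitor holds by-group data and could use them when judging the rule.

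The study is described as minimal risk and has no safety hypothesis. That limits how much rests on the point, but the protocol itself names overdose as a concern and sets a safety stopping rule.

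That a blinded research assistant collects all data does not close the gap. The statement belongs to the assessment schedule, which has no side-effect or overdose item, and section VII leaves the coach route open.

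**Conclusion.** The point holds for post-discharge medication side effects and non-fatal overdose. Followed as written, the plan detects these with different intensity in the two arms, and the expected direction is a relative over-count in the intervention arm.

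This is an expectation, not a certainty. A reader might infer that the intervention arm is bound to show more events, but with 29 per arm chance could reverse the order: at 0.9 against 0.8 the intervention count is higher with probability only 0.57. Likewise, control-arm events could be missed; the documents do not establish that they would be. In the illustration the ratio runs from 1.125 to 2.25 when the true ratio is 1. Its size rests on assumed detection rates and, for the contact counts, on an unstated coaching duration. Suicidal ideation and readmission are less affected.

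**What to change.** Add one row to Table 3: the same short questions in both arms at 4, 12 and 24 weeks, asked by the blinded research assistant, covering medication side effects and non-fatal overdose since the last visit, and emergency visits if the ASI and GAIN items do not already cover them.

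In IX.7, state that the primary by-group safety comparison uses these scheduled reports plus the PHQ-9 and readmission items already collected in both arms. Show visit completion and deaths by group beside it. Tabulate coach-detected and spontaneous reports separately, with the source recorded. Leave the existing routes for reporting individual events unchanged.

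The cost is one short form, a few minutes at each of three existing visits, and wording in IX.7. Two weaknesses remain. Recall over the 8- and 12-week intervals will be imperfect and may differ between arms, since coached participants may discuss events weekly. Participants who do not attend contribute no scheduled report, which is why completion and deaths should be shown by group.
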